The Follow-up Phase will begin once a subject completes the planned number of cycles or in case of treatment extension, the investigator decides to end the treatment and the End-of-Treatment visit at 4 weeks after last dose ( $\pm 7$  days) is completed. Reasons for premature discontinuation of treatment are listed in Section 10.3. Subjects who discontinue before disease progression must continue to have disease evaluations according to the Time and Events Schedule (as of Amendment 5, refer to the Time and Events Schedule in [Attachment 4](#)). The Follow-up Phase will continue until death, lost to follow up, consent withdrawal, or study end, whichever occurs first.

Three data cutoff timepoints are planned:

- The first data cutoff is for an interim analysis 6 months after the last subject is randomized. This will be the basis for the analysis of the primary study endpoint of CR. All available data at the time of this data cutoff may be included in the interim analysis.
- The second data cutoff will occur 12 months after the last subject is randomized. This will be the basis for the analysis of the primary study endpoint of PD/death rate. All available data at the time of this data cutoff will be included in the Clinical Study Report.
- A third data cutoff will occur at the end of the study. The data collected will be reported in a Clinical Study Report.

- The end of the study will occur up to approximately 7 years after the last subject's first dose, following a decision by the sponsor to end the study based on data from the smoldering multiple myeloma Phase 3 study (SMM3001), or for reasons as outlined in Section 17.9.2, whichever occurs first.

Assessment of tumor response and disease progression will be conducted in accordance with the International Myeloma Working Group (IMWG) response criteria. An assessment of MRD will be conducted on bone marrow aspirate samples. Safety evaluations will include AE monitoring, physical examinations, electrocardiogram (ECG) monitoring, clinical laboratory parameters (hematology and chemistry), vital sign measurements, and Eastern Cooperative Oncology Group (ECOG) performance status. A QTc substudy will be conducted in a subpopulation of subjects at selected sites. Blood samples will be drawn for assessment of PK and biomarker parameters.

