#### 9.1.4. Follow-up Phase

The Follow-up Phase will begin once subjects complete the planned number of cycles, and no treatment extension will be given as per investigator's discretion. In case of treatment extension or treatment re-initiation, the same procedures are to be followed as outlined in Section 9.1.3 and Table 1 (as of Amendment 5, refer to Attachment 4). If included in the treatment extension, it is possible that subjects will have 2 Follow-up Phase portions of the study (1 after the planned 20 cycles, and 1 after the last dose in the treatment extension). As of Amendment 5, these additional protocol-specified Follow-up assessments should be conducted as specified in Attachment 4.

Reasons for premature discontinuation of study treatment are listed in Section 10.3. Subjects who discontinue before disease progression must continue to have disease evaluations at Week 5, Week 9, and then every 8 weeks for the first year, thereafter every 16 weeks according to the Table 1 (as of Amendment 5, refer to Attachment 4) until confirmed PD, death, the start of a new anticancer therapy, withdrawal of consent, lost to follow-up, or the end of the study. If subjects have not progressed to symptomatic MM, no other treatment for SMM or MM is allowed during the study. After progressive disease, follow-up for subsequent multiple myeloma therapy (including the response to the first subsequent multiple myeloma therapy), second primary malignancies, and survival status will be obtained at least every 6 months.

If the information is obtained via telephone contact, written documentation of the communication must be available for review in the source documents. If the subject has died, the date and cause of death will be collected and documented in the eCRF.

The end of the study will occur up to approximately 7 years after the last subject's first dose, following a decision by the sponsor to end the study based on data from the smoldering multiple myeloma Phase 3 study (SMM3001), or for reasons outlined in Section 17.9.2, whichever occurs first.

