#### 9.2. Efficacy

As of Amendment 5, refer to Attachment 4 for a description of study procedures for subjects who continue in the Treatment Extension Phase or who have discontinued treatment but remain in Follow-up. Disease assessments will be performed at Week 5, Week 9, and then every 8 weeks in the first year, thereafter every 16 weeks (including treatment extension/re-initiation phase) until disease progression. A window of  $\pm 7$  days before the scheduled assessment date is allowed. For subjects with treatment delays, disease assessments should be performed at the time of daratumumab administration, but do not need to be repeated if they were performed within 14 days before the actual treatment date. Disease progression, if based on laboratory results only, must be confirmed by a consecutive assessment.

Disease assessments will be performed by a central laboratory (unless otherwise specified) according to Table 1. Disease progression to symptomatic MM will be evaluated using the IMWG criteria (Rajkumar 2014). For subjects who discontinue study drug before disease progression, disease assessments should continue to be performed as scheduled until disease progression, death,

withdrawal of consent for study participation, or the end of the study. Disease assessments scheduled for treatment days should be collected before study drug is administered.

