### 10.3. Premature Discontinuation of Study Treatment

If a subject's study treatment must be discontinued before the end of the planned number of cycles or during treatment extension/re-initiation, **this will not result in automatic withdrawal of the subject from the study**. After treatment discontinuation, the subject will move into the Follow-up Phase. The End-of-Treatment Visit should be performed, and Follow-up visit assessments should continue as specified in [Table 1](#) (as of Amendment 5, refer to [Attachment 4](#)). If study treatment is discontinued for a reason other than disease progression, then disease evaluations will continue to be performed as specified in [Table 1](#) (as of Amendment 5, refer to [Attachment 4](#)).

A subject's study treatment must be discontinued if:

- The investigator believes that for safety reasons (eg, AE) it is in the best interest of the subject to discontinue study treatment
- The subject becomes pregnant
- The subject (or the subject's legally acceptable representative) withdraws consent for administration of study treatment
- The subject experiences unacceptable toxicity, including IRRs described in [Section 6.4.3](#)
- The subject missed more than 2 consecutive planned doses due to daratumumab-related AEs

- The subject experiences disease progression (please see below).

A subject who experiences a second primary malignancy that cannot be treated by surgery alone must be withdrawn from the study. However, a subject who develops a malignancy that can be cured surgically may continue to receive the assigned study treatment and should continue to be followed for subsequent progression of MM.

**Before subjects discontinue study treatment due to disease progression**, sites will document disease progression (for example by completing a disease progression form or by contacting the IWRS) as soon as possible and within 48 hours. The medical monitor will confirm that treatment should be discontinued. After confirmation from the sponsor, study treatment will be discontinued and the subject entered into Follow-up.

The primary reason for discontinuation of study treatment is to be recorded in the eCRF.

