#### **10.4. Withdrawal from the Study**

A subject will be withdrawn from the study for any of the following reasons:

- Lost to follow-up
- Withdrawal of consent for study participation
- Death
- The study investigator or Sponsor, for any reason, stops the study or stops the subject's participation in the study

Before a subject is considered lost to follow-up, every reasonable effort must be made by the study site personnel to contact the subject and determine the reason for discontinuation/withdrawal. The measures taken to follow up must be documented.

When a subject withdraws before completing the study, the reason for withdrawal is to be documented in the eCRF and in the source document. Study treatment assigned to the withdrawn subject may not be assigned to another subject. Subjects who withdraw will not be replaced. If a subject withdraws from the study before the end of the Treatment Phase, assessments outlined in the End-of-Treatment Visit should be obtained.

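### Protocol 10.3 withdraws subjects with certain second malignancies from the study itself, contradicting its follow-up rules and ending data collection in a group whose risk of death is probably raised

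*Protocol*

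**What the plan says.** Protocol Section 10.3 deals with stopping study treatment early. Its general rule is that "this will not result in automatic withdrawal of the subject from the study", and it adds: "If study treatment is discontinued for a reason other than disease progression, then disease evaluations will continue to be performed as specified in" Table 1. Later in the same section comes the exception: "A subject who experiences a second primary malignancy that cannot be treated by surgery alone must be withdrawn from the study". The next sentence concerns malignancies that surgery can cure. Those subjects may stay on treatment and "should continue to be followed for subsequent progression of MM".

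Other sections set the end of follow-up differently:

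- Section 3.1: "The Follow-up Phase will continue until death, lost to follow up, consent withdrawal, or study end, whichever occurs first".
- Section 9.2, for subjects who stop drug before progression: "disease assessments should continue to be performed as scheduled until disease progression, death", consent withdrawal or study end.
- Table 1 and Attachment 4: second primary malignancy, subsequent anti-myeloma therapy and survival are each marked in the Follow-up column.
- Section 9.1.4: after progression, information on subsequent therapy, "second primary malignancies, and survival status will be obtained at least every 6 months".

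Section 10.4 opens its list with "A subject will be withdrawn from the study for any of the following reasons" and does not name second malignancy. The PFS censoring rule in Section 9.2.2.2 does not mention withdrawal for this reason. SAP Section 2.5.1 analyses PD/death rate, PFS and OS in the ITT set, and SAP Section 5.1.2 plans no imputation.

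**The concern.** A subject with a new cancer that surgery alone cannot treat probably has a higher risk of death than before. If that diagnosis ends study participation, the time at risk stops because of prognosis, and later deaths are not counted in endpoints that include death. Such censoring is potentially informative, and its direction favours the drug: the PD/death rate comes out too low, and PFS and OS too long. Exposure differs widely by arm (Cycle 1 only in Arm C; 20 cycles with possible extension in Arms A and B). If second malignancy were related to exposure, the comparison of schedules would be affected too; the documents neither show nor exclude that. The outcome of an event that SAP Section 6.3.3 lists as being of clinical interest would also go unrecorded.

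**Working it through.** **The text.** The sentence after the withdrawal rule reserves progression follow-up for surgically curable malignancies. Literally, therefore, follow-up ends for the others. That conflicts with the opening of Section 10.3, with Sections 3.1 and 9.2, and with the Follow-up rows for survival and second malignancy. This part needs no arithmetic.

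**Design figures.** ln 2/0.346 = 2.00 years = 24.0 months and ln 2/0.185 = 3.75 years = 45.0 months, matching the stated medians. The stated 80% power for PD/death rate depends on accrual length, which the documents do not give. A normal approximation with null variance gives 80.3% for accrual over 0.75 year and 82.9% over 1 year, so 80% is attainable.

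**Inputs.** From the documents: 40 per arm, null rate 0.346, alternative 0.185, one-sided 0.10, analysis 12 months after the last randomization, study end up to about 7 years after the last first dose. Assumed: uniform accrual over 1 year (follow-up 1–2 years at the 12-month analysis, 7–8 years at study end); malignancy rate w of 1%, 2% or 5% per year; PD/death hazard λ before the malignancy and kλ after it, with k from 1 to 5.

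**Formulas**, for a subject with potential follow-up c, averaged over c and multiplied by 40:

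- observed person-years T = (1 − e^(−(λ+w)c))/(λ+w); observed events λT; subjects withdrawn before PD wT
- events lost = ∫₀ᶜ w·e^(−(λ+w)t)·(1 − e^(−kλ(c−t))) dt; person-years lost = events lost/(kλ)
- rate with full follow-up = (observed + lost events)/(observed + lost person-years)

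The observed rate is λ throughout. With k = 1 the full-follow-up rate is also λ, because withdrawal removes person-time in proportion to events.

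For type I error, λ is chosen so that the full-follow-up rate is 0.346. Arms are then simulated and H0 is rejected when (d/T − 0.346)/√(0.346/T) < −1.282, where d is the observed number of events. Without withdrawal this gives 0.09 with about 16.1 expected events per arm.

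**12-month analysis, per arm** (ranges run over k = 1 to 5)

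| w per year | Withdrawn before PD (λ = 0.185) | Events lost (λ = 0.185) | Full-follow-up rate when 0.185 is observed | Events lost (true rate 0.346) | Type I error |
|---|---|---|---|---|---|
| 1% | 0.5 | 0.07–0.25 | 0.185–0.189 | 0.1–0.3 | 0.09–0.10 |
| 2% | 1.0 | 0.14–0.50 | 0.185–0.193 | 0.2–0.6 | 0.09–0.11 |
| 5% | 2.5 | 0.35–1.22 | 0.185–0.204 | 0.6–1.5 | 0.09–0.15 |

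Example, w = 2%, k = 5: (9.51 + 0.50)/(51.4 + 0.54) = 0.193. The lost person-time barely affects power: 82.9% becomes 82.7%, 82.4% and 81.6%.

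**Study end, 7–8 years, per arm** (λ = 0.185)

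| w per year | Withdrawn before PD | Events lost | Full-follow-up rate when 0.185 is observed |
|---|---|---|---|
| 1% | 1.6 | 0.9–1.5 | 0.185–0.192 |
| 2% | 3.1 | 1.7–2.8 | 0.185–0.199 |
| 5% | 7.1 | 3.9–6.5 | 0.185–0.220 |

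Example, w = 5%, k = 5: (26.1 + 6.5)/(140.9 + 7.1) = 0.220.

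**The case against.** Several points on the other side carry weight.

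- **The 12-month effect could be read as severe.** A reader might infer type I errors of 0.13 or 0.19. Those follow from removing 0.02 or 0.04 per year of the 0.346 hazard exactly when each event would occur (0.9 or 1.9 events lost; observed rate 0.326 or 0.306). That requires every withdrawn subject otherwise to have had an event at once, which nothing in the documents supports. With a delay between malignancy and event, 0.13 needs about 5% per year and a threefold hazard, and 0.19 is not reached in the range above. Exclusion criterion 4, which bars most malignancies in the previous 3 years, also argues against a high early rate.
- **The primary analysis is done.** The Amendment 5 rationale says it has been described in a clinical study report. An amended sentence cannot change it.
- **Not all later progression data are lost through this rule.** Section 9.1.4 ends disease evaluations at a new anticancer therapy, which many of these subjects would receive. Its six-monthly follow-up applies only after progression. The pre-progression conflict rests on Sections 3.1 and 9.2, the rest of 10.3, and the Follow-up rows.
- **Section 10.4 does not exclude this withdrawal.** Its last item lets the investigator or sponsor stop a subject's participation for any reason. That leaves the conflict with Sections 3.1 and 9.2 in place.
- **Deaths are not irrecoverable.** Consent under Section 16.2.3 includes permission to obtain survival status. What is missing is any procedure for doing so after withdrawal.
- **The rule may have meant study treatment.** It sits in a section on stopping treatment. If so, the wording is an error and needs the same correction.

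**Conclusion.** The contradiction is plain on the text. Followed literally, the rule stops survival data, and progression data where evaluations would otherwise continue, for subjects whose risk of death is probably raised. That is potentially informative censoring of three ITT endpoints.

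The size rests entirely on the assumed malignancy rates, hazard multipliers and accrual. At the 12-month analysis it is probably small: about 0.1–1.5 events per arm, type I error about 0.09–0.15 at nominal 0.10, and no bias if the hazard is unchanged. The main effect is on the long-term data for which Amendments 5 and 6 extended the study: about 0.9–6.5 PD/death events per arm over 7–8 years, with an observed 0.185 corresponding to 0.185–0.22. These late PFS and OS results are estimates without a hypothesis test, so the harm is biased description rather than a false rejection. OS is not quantified separately, because the documents give no death rate. The change is worth making; confidence is high on the conflict and limited on its magnitude.

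**What to change.** Amend the Section 10.3 sentence so that these subjects remain in the Follow-up Phase, at least for survival, subsequent therapy and second-malignancy status, unless they withdraw consent. Reconcile it with Section 10.4 and with the Section 9.1.4 rule that ends disease evaluations at a new anticancer therapy, so that it is clear for whom those evaluations continue. State in the protocol and SAP how these subjects are censored for PFS and whether a later death counts as an event. For anyone already withdrawn under the rule, obtain survival status where consent allows. Whether study treatment stops is a separate matter, not addressed here.

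The cost is one protocol sentence, a short SAP rule, and contacts for a few subjects: about 1.6 to 7.1 per arm before progression over the whole study under the assumed rates.

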#### **10.4. Withdrawal from the Study**

A subject will be withdrawn from the study for any of the following reasons:

- Lost to follow-up
- Withdrawal of consent for study participation
- Death
- The study investigator or Sponsor, for any reason, stops the study or stops the subject's participation in the study

Before a subject is considered lost to follow-up, every reasonable effort must be made by the study site personnel to contact the subject and determine the reason for discontinuation/withdrawal. The measures taken to follow up must be documented.

When a subject withdraws before completing the study, the reason for withdrawal is to be documented in the eCRF and in the source document. Study treatment assigned to the withdrawn subject may not be assigned to another subject. Subjects who withdraw will not be replaced. If a subject withdraws from the study before the end of the Treatment Phase, assessments outlined in the End-of-Treatment Visit should be obtained.

#### **Withdrawal from the Use of Samples in Future Research**

The subject may withdraw consent for use of samples for future research (refer to Section 16.2.5). In such a case, samples will be destroyed after they are no longer needed for the clinical study. Details of the sample retention for research are presented in the main ICF.

### **11. STATISTICAL METHODS**

Statistical analysis will be done by the sponsor or under the authority of the Sponsor. A general description of the statistical methods to be used to analyze the efficacy and safety data is outlined below. Specific details will be provided in the Statistical Analysis Plan.

### 11.1. Subject Information

The main analysis populations are:

- ITT population, defined as randomized subjects
- Safety population, defined as randomized subjects who received at least 1 dose of study agent

The ITT population will be used to summarize the study population and characteristics and efficacy; and the safety population will be used to summarize the safety data.

### 11.2. Sample Size Determination

Two hypotheses will be tested:

1.  $H_0$ : CR rate  $\leq 15\%$   
 $H_a$ : CR rate  $\geq 35\%$
2.  $H_0$ : PD/death rate  $\geq 0.346/\text{patient-year}$  (median PFS  $< 24$  months)  
 $H_a$ : PD/death rate  $\leq 0.185/\text{patient-year}$  (median PFS  $> 45$  months)

This study will enroll 120 subjects (40/arm) in total. With 40 subjects per arm, each arm will have:

- 90% power to show that the true CR rate is 35% at a one-sided level of 0.05
- 80% power to show that the true PD/death rate is 0.185/patient year at a one-sided level of 0.1

If two or more treatment schedules are deemed to be effective, with 40 subjects per arm this study would have:

- 85% probability of identifying the arm with the higher CR
- 80% probability of identifying the arm with the lower PD/death rate

For the QTc substudy, assuming that the intrasubject standard deviation for change from baseline in QTc ( $\Delta\text{QTc}$ ) is 20 milliseconds and that the true difference in means is 5 milliseconds, a sample size of 25 evaluable subjects (completers) will have 80% power to show that the upper limit of the two-sided 90% confidence interval (1 sided upper 95% confidence interval) for the difference in mean QTc ( $\Delta\text{QTc}$ ) at each timepoint and baseline will be less than 20 milliseconds. To ensure 25 subjects are evaluable, the QTc substudy will enroll approximately 30 subjects.

### 11.3. Efficacy Analyses

The first primary efficacy analysis of CR rate will occur 6 months after the last subject has been randomized and will be considered as an interim analysis. The purpose of this analysis is to select an appropriate dose and schedule and enable the sponsor's decision to proceed to Phase 3.

The second primary efficacy analysis of PD/death rate will occur 12 months after the last subject has been randomized. The purpose of this analysis is to make a decision to either proceed to Phase 3 if at the interim analysis there was not enough evidence to do so or to confirm the decision made after the interim analysis to proceed to Phase 3.

Descriptive statistics will be used to summarize data. For continuous parameters, number of observations, mean, standard deviation, median, and range will be used. For discrete parameters, frequency will be summarized. For time to event parameters, Kaplan Meier estimates will be produced. When sample sizes are small, sample listings may be provided instead.

### **11.3.1. Primary Efficacy Endpoint**

The primary efficacy endpoints are:

1. CR rate: The number and proportion of subjects who achieve a CR in each arm will be summarized. An exact 90% confidence interval and an exact p-value for rejecting the null hypothesis that the CR rate is 15% will be calculated.
2. PD/death rate: The ratio of subjects with an event (PD or death) to the total follow-up for all subjects will be summarized. A 90% confidence interval and a p-value for rejecting the null hypothesis that the PD/death rate is 0.346 will be calculated.

### **11.3.2. Secondary Efficacy Endpoints**

The secondary efficacy endpoints are:

1. Minimal residual disease (MRD) rate: The number and proportion of subjects who have a negative MRD will be summarized for each treatment arm. An exact 90% confidence interval will also be calculated
2. Time to next treatment: The median TNT in each treatment arm will be estimated using the Kaplan-Meier method. A 90% confidence interval will also be calculated
3. Overall Response Rate defined as CR+PR rate: The number and proportion of subjects who achieve a CR or PR in each arm will be summarized. An exact 90% confidence interval will also be calculated.
4. PFS: The median PFS in each treatment arm will be estimated using the Kaplan-Meier method. A 90% confidence interval will also be calculated
5. Incidence of symptomatic MM with adverse prognostic features, which include International Staging System (ISS) Stage III (based on  $\beta$ 2-microglobulin and albumin) and adverse cytogenetic characteristics: The number and proportion of subjects with an incidence of symptomatic MM with adverse prognostic features will be summarized for each treatment arm. An exact 90% confidence interval will also be calculated
6. Response to first subsequent MM treatment will be summarized descriptively.
7. Overall survival rate

